3.5.6 Additional Assessments

The long form GDS is a 30-item self-report assessment used to identify depression, specifically in an elderly population. The GDS questions are answered "yes" or "no", instead of a 5-category response set. This simplicity enables the scale to be used with ill or cognitively impaired individuals. A score of 0 to 9 is considered normal, while a score > 9 suggests depression.

C-SSRS is a semi-structured interview designed to assess the severity and intensity of suicidal ideation, suicidal behavior, and non-suicidal self-injurious behavior over a

Confidential Page 58 of 95

specified time period (eg, lifetime at baseline and since last visit at the additional visits). The assessment is completed by study staff with appropriate clinical training at scheduled visits as shown in the schedule of assessments (Table 7). If, at any visit following the baseline visit, there are any "YES" answers on items 4, 5, or any of the behavioral questions, a risk assessment should be done by a qualified clinician to determine whether it is safe for the subject to continue participation in the study.

The modified HIS is a clinical tool used for screening to differentiate vascular dementia from degenerative forms of the disorder (MCI, AD). Subjects with a score of 7 or higher are more likely to have vascular dementia. A low HIS is less likely to indicate vascular dementia because ischemic lesions severe enough to produce dementia would be expected to be severe enough to cause the accompanying neurologic changes and elevation in the index (Hachinski et al. 1975).

Trail making test is a neuropsychological test of visual attention and task switching. For part A, subjects connect a set of 25 sequentially numbered dots in order as fast as possible while still maintaining accuracy. For part B, subjects are asked to follow the same instructions but alternate between letters and numbers keeping each set in order. This will be conducted at baseline only.

The additional blood draw at ET/week 78 visit will be used to provide samples for assessment of blood-based biomarkers that may reflect neurodegeneration. Markers to be measured may include A-beta 1-40, A-beta 1-42, total tau, pTau 181, pTau 217 and neurofilament light chain (nfl).

3.5.7 Pharmacokinetic Assessments

A total of 3 samples will be collected for PK analysis at weeks 26, 52, and 78. In addition, approximately 40 mL of blood will be collected for screening and the end-of-study clinical laboratory evaluations. The total volume of blood collected will not exceed 300 mL.

Blood samples (1 mL x 4 mL) will be collected in Vacutainer tubes containing dipotassium ethylenediaminetetraacetic acid as a preservative at 4 hours to 7 hours after dosing with AGB101 or placebo. The time and date of collection for each sample will be recorded.

Blood samples will be centrifuged at approximately 3000 revolutions per minute (rpm) for 10 minutes at 4°C. The resulting plasma samples will be harvested and transferred into approximately equal portions into 2 appropriately labeled polypropylene screw-cap tubes labeled "A" and "B". PK samples will be placed in a freezer at -20°C or lower within 60 minutes of the blood draw.

Procedures for storage and shipment of the PK samples are provided in the PK Manual.

Confidential Page 59 of 95

3.5.8 Appropriateness of Measurements

All assessments that will be used in this study are commonly used, standard measurements frequently employed in studies investigating MCI and AD.

Confidential Page 60 of 95

4 ADVERSE EVENT REPORTING

Throughout the course of the study, all AEs will be monitored and recorded on an AE eCRF, including the AE's description, start and end date, outcome, seriousness, severity, action taken, and relationship to the study drug. If AEs occur, the first concern is the safety of the study subjects. All AEs will be followed until resolved or stable and the outcome documented on the eCRF.

4.1 Definitions and Criteria

4.1.1 Adverse Events

Per International Conference on Harmonisation (ICH) E2A: An AE is any untoward medical occurrence in a subject or clinical investigation subject administered a pharmaceutical product and which does not necessarily have to have a causal relationship with this treatment. An AE can therefore be any unfavorable and unintended sign (including an abnormal laboratory finding, for example), symptom, or disease temporally associated with the use of a medicinal product, whether or not considered related to the medicinal product.

Events meeting the definition of an AE **include**:

- Exacerbation of a chronic or intermittent pre-existing condition including either an increase in frequency and/or intensity of the condition
- New conditions detected or diagnosed after investigational product administration even though it may have been present prior to the start of the study
- Signs, symptoms, or the clinical sequelae of a suspected drug interaction
- Signs, symptoms, or the clinical sequelae of a suspected overdose of either investigational product or a concomitant medication

Clinically significant abnormal findings (laboratory test results, vital signs, physical examination findings, ECGs, radiologic exams, or other studies) should be recorded as AEs. A "clinically significant" finding is one that affects clinical management, including additional visits, monitoring or referrals, diagnostic tests or alteration of treatment, or that is considered clinically significant by the investigator. A clinically significant finding may be a change in a test that has previously been abnormal but now requires additional action.

When a medical or surgical procedure is performed, the condition that leads to the procedure should be recorded as the AE.

Events that **do not** meet the definition of an AE include:

• Anticipated day-to-day fluctuations or expected progression of pre-existing disease(s) or condition(s) present or detected at the start of the study unless

Confidential Page 61 of 95

judged by an investigator to be more severe than expected for the subject's underlying condition

- Abnormal laboratory, ECG, or vital sign measurements that are not labelled clinically significant (see definition above)
- Situations where an untoward medical occurrence did not occur (social and/or convenience admission to a hospital)
- Pregnancy
- Overdose in the absence of other AEs will not be reported as an AE in its own right

Changes in C-SSRS during the course of the study indicating worsening should be evaluated by the investigator for clinical significance, and if clinically significant (eg, alteration in medical care or intervention is required), an associated AE should be recorded, if present. The AE should be the primary underlying clinical manifestation assessed as clinically significant, and not the change in score itself.

Change in cognitive functioning (improvement or worsening) is also not considered to be an AE, since it is related to the underlying disease and the condition under study.

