3.4.7 Prior and Ongoing Medical History and Treatments

3.4.7.1 Prior and Ongoing Medical History

Investigators should document all significant medical history that subjects experienced within 12 months of screening. Any illness present at the time informed consent is given should be regarded as concomitant illnesses. Illnesses first occurring or detected during the study and/or worsening of a concomitant illness during the study should be documented as AEs in the eCRF.

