4.2 Reporting Procedures and Requirements

4.2.1 Adverse Events

AE recording will begin at the first screening visit. Thereafter, AEs will be ascertained by asking the subject (and study partner) how he/she has been since the last visit. Any

Confidential Page 64 of 95

AEs/SAEs occurring before the start of treatment (ie, before the first dose of the study drug) will be recorded and reported as such.

Also, the sign, symptom, or disease present before starting the treatment period are only considered AEs if they worsen after starting the treatment period.

If the investigator detects an AE in a study subject within 1 month of the last scheduled follow-up visit and considers the event possibly related or related to prior study treatment, the investigator should report it to WCT.

The investigator should report all information about AEs on the AE/SAE section of the electronic data capture (EDC) system. Whenever possible, an AE will be reported using a diagnostic term (eg, "common cold" or "upper respiratory infection" rather than "runny nose, cough, mild fever") and should be described with the attributes described in Section 4.1.4.

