5.2.7.2 Adverse Events

AEs will be summarized by treatment group and by maximum dose, latest dose received prior to the onset of the AE, by visit and treatment period.

A TEAE is defined as any AE that has an onset on or after the first dose of study drug, or any pre-existing condition that has worsened on or after the first dose of study drug, regardless of the causal relationship to the study drug. TEAEs will be attributed to a treatment using the following rules:

All analyses of AEs will be performed by the study period, so that it is possible to identify AEs that may be related to withdrawal from study treatment. The summaries of AEs will be limited to TEAEs. For summaries of TEAEs, a TEAE will be assigned to a given period if the date of onset of the TEAE is on or after the date of the first visit during the period but before the date of the first visit of the next period.

If the relationship of the AE to study drug is missing, it will be assumed to be related to the study drug for analysis purposes.

The incidence of subjects reporting TEAEs, treatment-emergent SAEs, TEAEs related to study treatment, treatment-emergent SAEs related to study treatment, and TEAEs leading

Confidential Page 73 of 95

to study discontinuation will be summarized using counts and percentages. The total number of TEAEs, treatment-emergent SAEs, TEAEs related to study treatment, treatment-emergent SAEs related to study treatment, and TEAEs leading to study discontinuation will also be summarized.

AEs will be coded using MedDRA. The incidence of TEAEs and treatment-emergent SAEs will be summarized at the subject level by MedDRA primary system organ class and preferred term using counts and percentages.

The incidence of TEAEs and treatment-related TEAEs will also be summarized by maximum severity and by closest relationship to study drug by MedDRA primary system organ class and preferred term. The summary will include the total number and percentage of subjects reporting a particular event. In counting the number of events reported, a continuous event, ie, an event reported more than once and which did not cease, will be counted only once; non-continuous TEAEs reported several times by the same subject will be counted as multiple events.

The incidence of TEAEs resulting in dose reduction will be summarized by the latest dose received and also by treatment group.

Withdrawal-related events will be tabulated separately.

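### Sections 4.1.1 and 4.2.1 disagree on whether a condition present but undiagnosed before the first dose, found on study and not worsened, is an adverse event

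*Combined protocol and SAP*

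**What the plan says.** Four parts of the protocol bear on a diagnosis made for the first time after dosing.

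- **Section 4.1.1**, the AE definition, lists among the events that qualify: "New conditions detected or diagnosed after investigational product administration even though it may have been present prior to the start of the study".
- **Section 3.4.7.1**, on medical history, has two consecutive sentences. The first reads "Any illness present at the time informed consent is given should be regarded as concomitant illnesses". The second reads "Illnesses first occurring or detected during the study and/or worsening of a concomitant illness during the study should be documented as AEs in the eCRF".
- **Section 4.2.1**, on recording AEs, first deals with the period before dosing ("AEs/SAEs occurring before the start of treatment (ie, before the first dose of the study drug) will be recorded and reported as such"). It then adds that "the sign, symptom, or disease present before starting the treatment period are only considered AEs if they worsen after starting the treatment period".
- **Section 5.2.7.2**, on AE analysis, says "A TEAE is defined as any AE that has an onset on or after the first dose of study drug", and adds pre-existing conditions that have worsened since then. It continues: "The summaries of AEs will be limited to TEAEs".

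Two further sections set the consequences. Section 4.2.2 applies the seriousness criteria to each AE, and the 24-hour report follows from that step. The end of section 5.2.7.2 promises a full listing of AEs and narratives for serious ones, neither restricted to treatment-emergent events (TEAEs).

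**The concern.** The definition and the recording rule use different tests. Section 4.1.1 asks when the condition was found. Section 4.2.1 asks when it was present. For most events the two tests agree. They part for disease that was already there but unknown, and such diagnoses are foreseeable here. Subjects are 55 to 85 years old, are followed for 78 weeks, and have chemistry, blood count, thyroid and liver panels at weeks 26, 52 and 78, with examinations at every clinic visit.

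Section 4.2.1 is the operational text on recording AEs, so a site may well work from it. A site that applies its words exactly would leave the condition off the AE form and would not reach the seriousness check in 4.2.2. With about 98 sites for 160 subjects (160 / 98 = 1.6 per site on average), the reading is made separately in many places, so the same kind of finding could be recorded at one site and not at another.

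**Working it through.** The documents give no rate or other figure for this point, so there is nothing to recompute. The check is to apply each rule to defined cases.

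| Case | 4.1.1 | 3.4.7.1 | 4.2.1 | 5.2.7.2 |
|---|---|---|---|---|
| A. Present but undiagnosed before the first dose, found after dosing, **not worsened** | AE | AE by the second sentence; concomitant illness by the first, if present at consent | Not an AE | TEAE if onset is taken as the detection date; not a TEAE if onset is the estimated start of disease |
| B. As A, but **worsened** after dosing | AE | AE | AE | TEAE |
| C. **Known** before the first dose, stable | Not a new condition | Concomitant illness, if present at consent | Not an AE | Not a TEAE |
| D. Arises and is **noticed between consent and first dose** | Not reached by the after-dosing item | AE | Recorded as a pre-treatment AE | Not a TEAE unless it worsens |

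Only case A produces a conflict.

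1. *Is there a tie-break?* No section says whether the definition in 4.1.1 or the recording rule in 4.2.1 prevails. Section 4.2.1 does not restrict its sentence to conditions known at the time, and neither does the consent sentence in 3.4.7.1.

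2. *What follows if a site uses 4.2.1?* The condition is not recorded as an AE. The seriousness step in 4.2.2 begins from an AE, so on that reading it is not taken.

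3. *What follows if a site uses 4.1.1?* The condition is recorded, with a start date, which section 4 requires on the AE form. No text defines that date for a newly diagnosed disease. If the site enters the date of detection, the event is a TEAE and is tabulated. If it enters an estimated earlier date and there is no worsening, the event is outside the AE summaries but remains in the listing.

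The conflict at step 2 affects whether data are collected at all. The question at step 3 affects only how collected data are classified.

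**The case against.** The best defence is that the sections can be read together. Section 4.1.1 is the definition and addresses this very case. The sentence in 4.2.1 follows directly on the rule for pre-dose events and can be taken to mean baseline conditions already identified. On that reading the specific rule governs and nothing is lost. That may well be what was intended, but 4.2.1 does not say so, and a site that follows its words is not misreading it.

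The defence is stronger on reach, and there it stands:

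- Worsened disease is captured under every section (case B).
- Section 4.1.1 separately requires clinically significant laboratory, ECG, examination and imaging findings to be recorded as AEs, and the condition behind any medical or surgical procedure likewise.
- Section 4.1.2 defines a serious event from the occurrence itself, with no worsening condition. It names malignancy among important medical events and makes an admission for diagnostic work-up reportable.
- Baseline screening (ECG, examinations, blood tests, a physician-read MRI and the thyroid exclusion) reduces the amount of undetected disease at entry.

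A reader might infer that a newly found cancer needing admission would go unreported. The documents do not support that as the expected result: 4.1.1 and 4.1.2 each offer a route to reporting, and a tumour that now needs admission will often have worsened. A reader might also infer that such events vanish from all outputs or from the DSMB's view. They do not once recorded. The listing and serious-event narratives are not limited to TEAEs, and section 6.6 gives the DSMB AEs and clinical laboratory data, again without that limit.

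**Conclusion.** The contradiction is literal and should be removed. It covers one class of event: a condition present but undiagnosed before the first dose, detected after dosing and not worsened. For that class, 4.1.1 and one sentence of 3.4.7.1 require an AE, while 4.2.1 and the adjacent sentence of 3.4.7.1 point the other way. An event is lost altogether only if a site follows 4.2.1 and none of the other routes in 4.1.1 or 4.1.2 brings it in.

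The number of events cannot be given. The documents state neither how often such diagnoses occur nor how sites read the text, and a count built on guessed proportions would carry no weight. Allocation is randomised and double-blind, so there is no evident reason for the loss to differ between arms. The issue is incomplete and inconsistent safety capture, with no claim of bias for or against the drug and no effect on the primary efficacy analysis.

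The treatment-emergence question is secondary. Section 5.2 leaves detail to an SAP to be finalised before database lock, and that SAP can set the onset convention. It cannot recover events that sites never recorded, so the collection rule has to be corrected in the protocol.

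**What to change.** - **Section 4.2.1:** limit the rule that earlier disease counts only on worsening to conditions *known* before the first dose. Known is preferable to known and documented: 3.4.7.1 asks only for significant history within 12 months of screening, so a documentation test could turn old, known history into AEs.
- **Section 3.4.7.1:** limit the concomitant-illness sentence to illnesses *known* at consent. Changing 4.2.1 alone would leave this section in conflict with itself and with 4.1.1.
- **SAP, with section 5.2.7.2:** state which date counts as onset for a condition first detected on study, for example the date of first detection. This is a choice of convention, since it would tabulate as treatment-emergent some disease that began before dosing. The aim is that every site's events are classified in the same way.

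The cost is three short wording changes and a matching line in the form-completion instructions. Slightly more AEs would be recorded, in both arms.

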3.5.5 Safety Assessments

3.5.5.1 Physical Examination

Physical examinations will include examining the general appearance, skin, neck (including thyroid), eyes, ears, nose, throat, heart, lungs, abdomen, lymph nodes, extremities, and nervous system. Neurological examinations will include examination of coordination, gait, patellar deep tendon reflexes, sensation, strength and muscle tone, and orientation. An AE form must be completed for all changes identified as clinically noteworthy. Height without shoes will be recorded in inches or meters at screening.

Confidential Page 57 of 95

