5.2.7.6 Other Variables Related to Safety

Change from baseline in C-SSRS is another endpoint related to safety. Changes in C-SSRS during the course of the study indicating worsening should be evaluated by the investigator for clinical significance, and, if clinically significant (eg, alteration in medical care or intervention is required), an associated AE should be recorded, if present. The AE should be the primary underlying clinical manifestation assessed as clinically significant, and not the change in score itself.

Confidential Page 75 of 95

AgeneBio, Inc.

Changes from baseline in physical and neurological examinations are additional endpoints related to safety that will also be evaluated by the investigator for clinical significance, and, if clinically significant (eg, alteration in medical care or intervention is required), an associated AE should be recorded.

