6.6 Data Safety and Monitoring Board

The DSMB will meet periodically to review all the safety study data (AEs and clinical labs) by group, with the groups identified only as group A and group B (ie, DSMB members will be blinded to the treatment assignment). The DSMB will not see any efficacy data. If, during the course of the data review, the DSMB observes a separation of the two groups on any safety measure that suggests a pattern of AEs, the DSMB can request information on group assignment from the sponsor. If there is a difference between groups on some important safety finding, the DSMB can request information on group assignment. If no such difference emerges between groups, the DSMB will remain blinded to the treatment assignment until the last subject visit. A description of the

Confidential Page 78 of 95

DSMB composition, its charter, and methods of analyses and communication will be provided in a companion document.

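### Section 4.1.1 excludes cognitive worsening from adverse events without the exception it gives other disease progression, so non-serious acute confusion could be under-counted

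*Combined protocol and SAP*

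**What the plan says.** The exclusion stands in Section 4.1.1, after the paragraph on the C-SSRS: "Change in cognitive functioning (improvement or worsening) is also not considered to be an AE, since it is related to the underlying disease". It makes no distinction by onset, severity or suspected cause.

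Other parts of the protocol bear on the same events:

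- **4.1.1, list of what is not an AE.** Expected progression of an existing disease is excluded unless it is "judged by an investigator to be more severe than expected for the subject's underlying condition".
- **4.1.1, findings.** "Clinically significant abnormal findings (laboratory test results, vital signs, physical examination findings, ECGs, radiologic exams, or other studies) should be recorded as AEs". Exacerbation of a pre-existing condition is also listed as an AE.
- **3.5.5.1.** "Neurological examinations will include examination of coordination, gait, patellar deep tendon reflexes, sensation, strength and muscle tone, and orientation". The next sentence reads: "An AE form must be completed for all changes identified as clinically noteworthy".
- **5.2.7.6.** "Changes from baseline in physical and neurological examinations are additional endpoints related to safety that will also be evaluated by the investigator"; a clinically significant change should have an associated AE.
- **3.4.7.1 and 4.2.1.** Worsening during the study of an illness present at consent is documented as an AE. Signs, symptoms or diseases present before treatment count as AEs only if they worsen after it starts.
- **5.2.7.2.** A TEAE is an AE that starts after first dose, or a pre-existing condition that worsens after it. AE summaries are restricted to TEAEs.
- **6.6.** "The DSMB will meet periodically to review all the safety study data (AEs and clinical labs) by group". The DSMB gets no efficacy data. Its charter and methods are in a companion document.

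**The concern.** The sentence attributes all cognitive change to the disease before any comparison of arms. The general definition in 4.1.1 requires no causal link, and 4.1.4 treats timing alone as enough for a plausible association. In a randomised trial, attribution comes from comparing the arms, and events that never reach the AE form cannot be compared.

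Safety and tolerability is a stated objective (2.5), the drug acts on the central nervous system, and the subjects are cognitively impaired. If sites do not record acute confusion, a low count would not support a claim of cognitive tolerability. The DSMB could not make up the gap from CDR or MMSE, because it does not see them.

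**Working it through.** There is no figure in the plan to reproduce. The check is a comparison of rules, followed by a count of the routes by which an event could still be captured.

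**1. One event under each rule.** Suppose a subject is newly disoriented at the week 13 visit, and the event is clinically significant but not serious. Table 7 schedules a neurological examination at that visit.

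| Rule | Result |
|---|---|
| 3.5.5.1, noteworthy examination change | AE form required |
| 5.2.7.6, clinically significant examination change | AE to be recorded |
| 4.1.1, clinically significant finding | AE to be recorded |
| 3.4.7.1 and 4.2.1, if seen as worsening of an existing illness | AE |
| 4.1.1, sentence on cognition, read literally | Not an AE |

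No section says which rule prevails.

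**2. Does the exception carry over?** The exception for unexpectedly severe progression sits in a separate bullet on pre-existing conditions. The sentence on cognition stands apart and does not refer to it. The C-SSRS paragraph just before it tells the investigator to record the underlying clinical manifestation; the sentence on cognition has no such instruction.

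**3. Following the event forward.** Section 4 has AEs entered on an AE form. An episode that is not entered does not reach the TEAE tables (5.2.7.2) or the AE data given to the DSMB (6.6). The second part of the TEAE definition, a worsened pre-existing condition, does not require in its wording that the event first be called an AE. The loss is therefore not automatic by definition. However, the supplied text names no source for that part other than the AE form.

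**4. Other routes.** Table 7 has nine scheduled post-baseline contacts: weeks 1, 13, 17, 26, 39, 52, 56, 65 and 78.

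- AE questioning: 9 of 9.
- Examination including orientation: 6 of 9 (weeks 13, 26, 39, 52, 65, 78), and at early termination.
- CDR, MMSE and FAQ: 3 of 9 (weeks 26, 52, 78), and at early termination. So 9 − 3 = 6 contacts have no cognitive scale, and the first with one is day 182.

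Sustained worsening would show by arm in the efficacy data. A brief episode between major visits depends on questioning and examination, and whether their findings become AEs is what the sentence leaves in doubt.

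**5. Scale, for illustration.** Let s be the share of true events that sites record. The documents give no value for s. With 0 recorded among 80 in an arm, the one-sided 95% upper limit on the true risk is (1 − 0.05^(1/80))/s = 0.0368/s:

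| Assumed s | Upper limit |
|---|---|
| 1 | 3.7% |
| 0.5 | 7.4% |
| 0.25 | 14.7% |
| 0 | none |

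**6. Evidence on the drug.** Section 1.5 lists confusion and mental slowing as possibly related AEs in a pharmacokinetic study of epilepsy patients, many of them elderly, with no placebo group described. In the placebo-controlled add-on epilepsy studies, confusion and abnormal thinking were at least as common on placebo, at 1000 to 3000 mg/day; amnesia was 2% against 1%. A review of safety data found more AEs in epilepsy subjects than in elderly subjects with cognitive disorders, who received lower doses. None of this establishes an excess at 220 mg.

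**The case against.** The strongest reply is that the sentence carries its own limit. Its reason is "since it is related to the underlying disease and the condition under study", and acute drug-related confusion falls outside that reason. The word *also* ties it to the preceding text, where the AE is the clinical event and not the change in score. On that reading only measured cognition is excluded. Investigators must in any case complete an AE form for a noteworthy change in orientation, they ask about AEs at every contact, and the TEAE definition takes in worsened conditions. The DSMB's methods are in a document not supplied, and Section 5.2 leaves analysis detail to a separate SAP.

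Much of this stands. The narrower reading is reasonable and the other routes are real, so the loss is a possibility and not a certainty. What remains is that the sentence speaks of cognitive functioning, not of scores, and that no rule settles the conflict. With about 98 sites planned, different readings are likely enough to be worth preventing.

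A reader might infer that serious events are lost too. The documents do not support that: 4.1.2 defines serious events by any untoward medical occurrence, so a hospitalised delirium should still be reported, although the procedure in 4.2.2 does start from events already called AEs.

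**Conclusion.** The inconsistency is real and its consequence is limited. Non-serious acute confusion or disorientation could be under-counted in the TEAE tables and in the AE data the DSMB reviews, to the extent that sites follow the sentence literally. That extent is unknown; the shares in the illustration are assumptions, and no event count can be projected.

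Two stronger readings are tempting. One is that cognitive harm is removed from the trial altogether. It is not: examinations, AE questioning and the efficacy scales all remain, and sustained worsening would be visible by arm at the end. The other is that the drug causes confusion and the plan conceals it. The documents show no excess on the drug. No efficacy estimate or test is affected. This is a cheap improvement to AE recording.

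**What to change.** Replace the sentence in 4.1.1 with:

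> Expected gradual decline in cognition, including change in CDR, MMSE, FAQ, ISLT or BPS-O scores, is not an AE. New or acute confusion or disorientation, or cognitive worsening judged by the investigator to be more severe than expected for the underlying condition, is recorded as an AE.

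Send a memo to the sites. Summarise these AEs by arm in the safety analysis set; as AEs they then reach the DSMB without a new data flow.

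Two further triggers are best left out. Fluctuating confusion would collide with the exclusion of anticipated day-to-day fluctuation in 4.1.1. Worsening that leads to stopping study drug would overlap with the lack-of-efficacy reason in 3.3.3.

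The cost is one sentence, a memo and one AE grouping, with no new visits or tests. Some disease-related events will be recorded as AEs, possibly more on placebo if the drug works, so an imbalance would need careful reading. Counts before and after the change are not comparable and should be shown separately. The summary should stay descriptive: with 80 per arm, two-sided Fisher exact tests give p = 0.059 for 5 against 0 and p = 0.028 for 6 against 0, so small differences will rarely be conclusive.
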